12.4.6 ECHO-cardiography

ECHO-cardiography will be performed as part of Examinations 1-5. It is planned to perform transthoracic ECHO-cardiography and transesophageal intraoperative ECHO-cardiography. The scope of the study during Examinations 1, 3-5 will correspond to the minimum transthoracic EAUD protocol (https://easud.org/sites/default/files/manuals/tte_protokol_eaud.pdf). Examination 2 may be significantly hindered due to unsatisfactory visualization. All DICOM images obtained during the examination of each study participant will be stored in RAW format on a common DICOM server for all research centers. A selective cross-analysis of the standardized set of DICOM data, in accordance with EAUD, is planned to be conducted by physicians with more than 5 years of experience in cardiovascular imaging in the ultrasound modality.

- *The assessment of myocardial contractility will be performed using the Simpson Biplane method, the General Electric “auto EF” algorithm, and Speckle Tracking analysis based on General Electric algorithms.*
- *The standard transthoracic protocol in all cases will be supplemented by myocardial strain analysis with the recording of initial RAW DICOM data, as well as Global Longitudinal Strain, Strain Rate, and myocardial mechanical dispersion.*

12.4.7 Questionnaires

1. *EuroQOL-5D (EQ-5D):* EQ-5D is a standardized instrument for assessing the respondent's quality of life: in the form of a health profile - five questions (mobility, self-care, usual activities, pain/discomfort, anxiety/depression), each with five levels of severity, and a score obtained using the EQ-VAS visual analog scale.

The questionnaire will be offered for completion during Examinations 1 and 3-5. The questionnaire is available only in Russian. Patients who do not have proficiency in Russian at the level of writing and reading will be excluded from periodic testing.

12.4.7 6-Minute Walk Test

This test is one of the methods for diagnosing heart failure, but it is used more for determining the functional class rather than confirming it. It also involves determining the endurance of patients to assess the effectiveness of therapy.

The test is easy to perform, does not require complex equipment, and can be conducted both in inpatient and outpatient settings. The test allows for the assessment of patients' daily activity levels, and its results correlate well with quality-of-life indicators; moreover, they can be used as additional criteria for evaluating the effectiveness of treatment and rehabilitation of patients.

The methodology for conducting this test involves using a straight corridor familiar to the patient, with zero incline and length markings every 3 meters, and separate markings for turnaround points are provided. After a preliminary rest period of 10 minutes, the subject's pulse rate and blood pressure are measured. If there are no contraindications to performing the test, the subject is instructed to cover the maximum distance in 6 minutes, without running or sprinting, but a reduction in walking pace and short breaks are allowed. The time interval is measured by starting a countdown timer, which loudly signals with a sound at the end of 6 minutes. The doctor assesses the distance covered and the functional class.

13.11 Definition of the term 'End-of-study'

The date of completion of the study is considered to be the day on which the last subject included in the study underwent Examination 5.

Other aspects of study completion

The principal investigator has the right to terminate the study at any time based on clinical or organizational considerations, while ensuring the interests of the study participants are protected.

The completion of the study will be reported to the local ethics committee within 90 days, or within 15 days if there was an early termination of the study. All researchers will inform the study participants about the premature termination, ensuring the continuation of qualified dynamic monitoring for previously included participants.

A report on the conducted study will be compiled within 12 months from the date of study completion.

15. PROTOCOL COMPLIANCE

The researchers ensure compliance with the study protocol. In case, the researcher believes that a deviation from the protocol will optimize the study process or allow for obtaining extremely significant additional results, this should be considered an amendment to the protocol. If this amendment is not approved by the local ethics committee, it cannot be implemented. Thus, all proposed deviations from the protocol must be reported to the principal investigator and the local ethics committee. If approved, the changes made will be reflected in the 'History of Changes' section of the research protocol.

15.1 Amendments to the Protocol

Any changes to the protocol must be agreed upon in writing with the principal investigator and the local ethics committee. The above does not apply to protocol changes aimed at the immediate safeguarding of the health and safety of the research participant. The principal investigator should be notified of this fact within 10 working days.

16. ACCESS TO STUDY DATA

Direct access will be provided to authorized representatives of the institutions where the study is conducted, as well as regulatory officials for monitoring, auditing, and inspections related to the study.

17. DATA PROCESSING AND STORAGE

17.1 Data collection, primary information, and individual registration cards (IRC)

All documentation related to the study, as well as information concerning the patients participating in it, is strictly confidential. The researcher must ensure the anonymity of the volunteers. In the IRK and other documents, volunteers should not be identified by their first and last names. The identification of volunteers is carried out using the first letters of the volunteer's last name, first name, and patronymic (FIO), date of birth (DD.MM.YYYY), and an individual number assigned to the volunteer upon inclusion in the study. Each volunteer is assigned a unique number by the Researcher, consisting of numeric and alphabetic designations, with the following structure: eight digits arranged sequentially from left to right, digits 1 to 6 are defined for this study by the following sequence: 11-RIS, which is the same for all volunteers, and the last two digits correspond to the serial number of the volunteer upon admission to the research center. Thus, the data provided by the Researcher for the identification of volunteers have the following format:

digits 1-3 - the first letters of the volunteer's last name, first name, and patronymic; digits 4-11 - the volunteer's date of birth (DD.MM.YYYY);

digits 12-19 - a unique number assigned to the volunteer by the Investigator responsible for conducting the clinical trial, consisting of numerical and/or alphabetical designations and entered into the Clinical Trial Protocol. The Investigator must maintain a separate Identification Log of individual numbers, last names, dates of birth, addresses, phone numbers, and medical documentation numbers (if available). The researcher must keep documents strictly confidential that are not intended for disclosure in general cases, in particular, signed Informed Consent Forms and the Identification Log.

The report and study documents will use only the initials, birth dates, and unique numbers of participant, which are part of the Individual Identification Code. The Individual Identification Code is established by the insurer after obtaining permission from the Ministry of Health and Social Development of the Russian Federation to conduct a clinical trial, based on the data provided by the Researcher of the volunteer participating in the clinical trial. The assigned individual identification code is not subject to change.

All data about the volunteer obtained during the study is first entered into the primary documentation (documentation of the medical institution or physician maintained at the research center) and then transferred to the Individual Registration Card of the volunteer.

Study protocol

The data contained in the IRK must match the data in the primary documentation. The IRK must be completed no later than 5 days after the volunteer's visit to the research center. The IRK is maintained in digital format. Logging of changes made is mandatory. The principal investigator bears the final personal responsibility for the accuracy and authenticity of all clinical, instrumental, and laboratory data entered into the IRK.

All records and documents related to the clinical study, including Individual Registration Cards, patient information sheets, and volunteer lists, are retained at the clinical institution where the study is conducted for 15 years after the study's completion.

18. ETHICAL ASPECTS

18.1 Ethical principles of conducting the study

The study will be conducted in accordance with the current version of the Declaration of Helsinki, the provisions of the National Standard of the Russian Federation GOST R52379-2005 on Good Clinical Practice dated April 1, 2006, and the Order of the Ministry of Health of the Russian Federation dated April 1, 2016. No. 200n 'On the approval of the rules of good clinical practice' and the provisions of Good Clinical Practice (GCP).

The material for conducting the study will be collected at two clinical sites: Petrovsky NRCS, Moscow and BUZ VO VOKB No.1, Voronezh.

By signing the study protocol, the researcher agrees to adhere to the instructions and procedures described therein, as well as the principles of Good Clinical Practice, which they comply with. Regulatory approval will be obtained in accordance with applicable regulatory requirements. All ethical and regulatory approvals must be obtained before the patient undergoes any study-related procedures, including screening tests to determine eligibility criteria.

Approval for conducting the study is planned to be obtained at both centers from the local ethics committee of the RCHC.

18.2 Approvals

The study protocol, informed voluntary consent form, individual patient registration card, and questionnaire forms must be approved by the local ethics committee and other regulatory officials, in accordance with current legislation, before the initiation of the study.

18.3 Informed Voluntary Consent

The investigator must obtain written informed consent from each participant prior to their participation in the study and before any study-related procedure is undertaken. Thus,

Study protocol

informed consent must be obtained at Examination 1 before performing any study-related procedure. Before this, the investigator or their representative must inform each participant about the objectives, benefits, risks, and requirements related to the study.

Only a qualified physician can obtain informed consent.

The participant will be provided with an information and consent form written in clear and simple manner. He/she should be given enough time to clarify the details of the study and make an informed decision about participation. The researcher must answer all relevant questions that may arise from the patient.

Two originals of the voluntary informed consent form must be completed, dated, and personally signed by the participant and the person responsible for obtaining informed consent. The participant will be provided with one signed original, and the second original will remain with the Investigator.

The obtaining of informed consent must be clearly documented in the participant's individual registration card. The following aspects must also be recorded in the subject's medical record:

- The date the informed consent form was provided to the subject.
- The date written informed consent was obtained.
- The name of the person who obtained the informed consent.
- Any other relevant information regarding the consent acquisition process.

Each patient included in the clinical study must have an individual participant card, which reflects data allowing the identification of the clinical study. (In particular, the study title, patient identifier in the study, date of signing the informed consent, 'date of completion of patient participation,' which must be filled in at Examination 5, the principal investigator's name, and the research group's contact number must be specified).

18.4 Patient Confidentiality

Researchers ensure the confidentiality of participants, who will be identified only by their subject identification number in any database. All documents will be stored in a secure location. The study was conducted in accordance with the 'Personal Data Protection' law.

19. FUNDING

The study is initiative-driven, and no sponsorship is provided.

20. CLINICAL TRIAL REPORT AND PUBLICATION POLICY

20.1 Clinical trial report

The clinical trial report must be prepared and signed by all study participants within 12 months after the completion of the study.

20.2 Publication Policy

The results of this study will be published in reputable medical journals. The information obtained may provide impetus for further research on reverse remodeling of the left ventricle in patients with chronic aortic regurgitation.

Principle investigator is responsible for publishing the data obtained in this study.

21. PROPOSED STUDY SCHEDULE

Start date: May 2024

End date: May 2029

Report preparation date: within 12 months from the end of the study

22. APPENDICES

22.1 Appendix 1. “EQ-5D Quality of Life Questionnaire”

Title in Russian: Quality of Life Questionnaire EQ-5D

Original title European Quality of Life Questionnaire (EQ-5D)

Source:

Rabin R, de Charro F. EQ-5D: a measure of health status from the EuroQol Group. Ann Med. 2001 Jul; 33(5): 337 - 43. doi: 10.3109/07853890109002087. PMID: 11491192.

Russian population health-related quality of life indicators calculated using the EQ-5D-3L questionnaire/E.A. Aleksandrova, A.R. Khabibullina, A.V. Aistov [et al.]//Siberian Scientific Medical Journal. - 2020. - Vol. 40. - No. 3. - P. 99 - 107. - DOI 10.15372/SSMJ20200314.

Type - questionnaire

Purpose: assessment of quality of life

English EQ-5D-Y-5L Paper Self-Complete

Under each heading, please choose the ONE answer that best describes your health TODAY.

MOBILITY (walking about)

I have no problems walking about

I have a little bit of a problem walking about

Study protocol

I have some problems walking about
I have a lot of problems walking about
I cannot walk about

LOOKING AFTER MYSELF

I have no problems washing or dressing myself
I have a little bit of a problem washing or dressing myself
I have some problems washing or dressing myself
I have a lot of problems washing or dressing myself
I cannot wash or dress myself

DOING USUAL ACTIVITIES (for example, going to school, hobbies, sports, playing, doing things with family or friends)

[figure not shown]
I have no problems doing my usual activities
I have a little bit of a problem doing my usual activities
I have some problems doing my usual activities
I have a lot of problems doing my usual activities
I cannot do my usual activities

HAVING PAIN OR DISCOMFORT

I have no pain or discomfort
I have a little bit of pain or discomfort
I have some pain or discomfort
I have a lot of pain or discomfort
I have extreme pain or discomfort

FEELING WORRIED, SAD OR UNHAPPY

I am not worried, sad or unhappy
I am a bit worried, sad or unhappy
I am quite worried, sad or unhappy
I am really worried, sad or unhappy
I am extremely worried, sad or unhappy

	The best health you can imagine

We would like to know how good or bad your health is TODAY.This line is numbered from 0 to 100.100 means the best health you can imagine.0 means the worst health you can imagine.Please mark an X on the line to show how your health is TODAY.Now, write the number you marked on the line in the box below. 
YOUR HEALTH TODAY = 
	

	The worst health you can imagine
--	---

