10.2 Study endpoints

Primary endpoints:

1. *Reduction of the left ventricle end-diastolic volume at 3 and 12 months after surgical correction of aortic regurgitation*
2. *Freedom from readmission for heart failure related conditions 12 months after surgery*

Secondary endpoints:

1. Patient quality of life according to the EQ-5D-5L questionnaire results.

Exploratory endpoints:

1. Left ventricle ejection fraction at 3 and 12 months after surgical correction of aortic regurgitation

2. Diastolic function of the left ventricle based on echocardiography results, assessed preoperatively and at 3 and 12 months after surgical correction of the aortic regurgitation (mean E/e', DT)
3. Indexed to BSA volume of the left atrium (according to transthoracic echocardiography results) preoperatively, as well as at 3 and 12 months after surgical treatment

*BSA – body surface area, calculated using the Mosteller formula

11. Study design

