11.2 Definition of the study group

Patients who have undergone open surgical correction of aortic valve insufficiency with large eccentric left ventricle remodeling (EDV more than 250 ml). Men and women over 18 years old.

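### The only secondary endpoint is the EQ-5D-5L in adults, but the only form in the protocol is labelled EQ-5D-Y-5L and nothing explains the difference

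*Protocol*

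**What the plan says.** Four places in the protocol bear on which quality-of-life instrument is used.

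- **Section 10.2 (Study endpoints)** gives a single secondary endpoint: "Patient quality of life according to the EQ-5D-5L questionnaire results".
- **Sections 11.2 and 11.2.1** set the population: "Men and women over 18 years old".
- **Section 12.4.7 (Questionnaires)** gives no version: "EQ-5D is a standardized instrument for assessing the respondent". It describes "five questions (mobility, self-care, usual activities, pain/discomfort, anxiety/depression), each with five levels of severity", together with a visual analogue score. The form is to be offered at Examinations 1 and 3 to 5. On language it states: "The questionnaire is available only in Russian". Patients who cannot read and write Russian are left out of the testing.
- **Section 22.1 (Appendix 1)** is titled simply as the EQ-5D, but the form in it is headed "English EQ-5D-Y-5L Paper Self-Complete". Its usual-activities item carries the examples "for example, going to school, hobbies, sports, playing, doing things with family or friends", and its last item is headed "FEELING WORRIED, SAD OR UNHAPPY".

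The secondary objective in section 10.1 relates the severity of preoperative mitral regurgitation to quality of life 12 months after surgery. Main objective 4 in the synopsis also concerns quality of life at 12 months.

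**The concern.** The endpoint and the appended form carry different version names, and the difference goes beyond the label. The form's wording departs from the protocol's own description of the domains, and its examples of everyday activity fit poorly with adults having valve surgery. Nothing elsewhere settles the matter. Section 12.4.7 and the appendix title say only EQ-5D, Table 1 says only that a questionnaire is completed, and one source cited in the appendix concerns a third version, the EQ-5D-3L.

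A site that looks in the protocol for the form finds only the Y version. If it used that form or had it translated, it would not collect the instrument named as the secondary endpoint. The form asks about health on the day of completion, so answers given on the wrong version cannot be collected again later. This applies above all to the answers given before surgery. With two sites, an unspecified version also leaves room for the sites to differ.

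**Working it through.** No power, error-rate or effect-size calculation is involved. The check is a comparison of the texts, followed by a count of the forms exposed.

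**Comparison**

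| Feature | Section 10.2 | Section 12.4.7 | Appendix 1 |
|---|---|---|---|
| Version named | EQ-5D-5L | EQ-5D, no version | EQ-5D-Y-5L on the form; EQ-5D in the title |
| Language | not stated | Russian only | English |
| Second item | not stated | self-care | looking after myself |
| Fifth item | not stated | anxiety/depression | worried, sad or unhappy |
| Examples of usual activities | not stated | none given | school, hobbies, sports, playing, family or friends; work is not named |
| Structure | five-level by its name | five items, five levels, visual analogue score | five items, five levels, 0 to 100 scale |

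Reading across the rows:

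1. The structure agrees. The five items correspond one to one, and the number of levels and the 0 to 100 scale match. The conflict is about version and wording, not about the number of items or levels.
2. The version names in section 10.2 and Appendix 1 differ. Section 12.4.7 cannot decide between them because it names neither.
3. The language differs between section 12.4.7 and Appendix 1. That suggests the printed page is not what patients will be handed, but it does not account for the difference in version. An English stand-in for a Russian EQ-5D-5L should still be an EQ-5D-5L.
4. Section 18.2 requires questionnaire forms to be approved by the ethics committee. It does not say which forms they are.

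**Forms exposed if the appended version, or a translation of it, is used**

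Inputs: 120 patients (synopsis, number of study subjects) and 4 questionnaire visits, namely Examinations 1, 3, 4 and 5 (Table 1 and section 12.4.7).

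- All forms: 120 × 4 = 480.
- Preoperative forms (Examination 1): 120 × 1 = 120.
- 12-month forms (Examination 5): 120 × 1 = 120.

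These are maxima for 120 patients. The true numbers would be lower, because patients without written Russian are not tested; the protocol does not say how many that will be.

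**Forms exposed if a Russian EQ-5D-5L is already in use:** 0.

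**Limits of the check.** The adult EQ-5D-5L form is not in the protocol, so the difference in wording is shown against the domain names in section 12.4.7, not line by line against that form. The protocol does not define the letter Y, and the argument does not depend on its meaning.

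**The case against.** The strongest reply is that the printed page cannot be the working form. It is in English, patients answer in Russian, and no section tells a site to administer or translate Appendix 1. The protocol reads like an English rendering of a Russian original, and forms go to the ethics committee separately, so a correct Russian form may well exist. On that view section 10.2 names the instrument, section 12.4.7 is consistent with it, and only an appendix page is out of place.

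Much of this stands. The harm is conditional and may be nil. What it does not do is explain the version. No section calls the page a stand-in, and naming an instrument in section 10.2 does not identify the form to be completed.

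Two narrower points have some force:

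- **Baseline.** The stated secondary objective rests on quality of life at 12 months, and section 10.2 does not define the endpoint as a change from baseline. Loss of the preoperative forms is therefore not the main exposure for that objective. The 12-month forms are, and they would be on the wrong version too.
- **The count.** The synopsis gives 120 patients but also asks for at least 64 per group. With two groups that is 2 × 64 = 128 patients and 128 × 4 = 512 forms. The figure of 480 is the maximum only for the stated 120. This conflict in the sample size is a separate matter and does not alter the point about the questionnaire.

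It could also be said that questionnaire details belong in a statistical analysis plan. Scoring may, but the instrument and the form are stated in the protocol, and there they disagree.

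**Conclusion.** The concern holds: Appendix 1 is wrong as written. The protocol attaches a form of one version to an endpoint defined on another and leaves the working form unidentified. The inconsistency is certain on the text. Its effect on data is not: between 0 and 480 forms, including up to 120 at 12 months, assuming 120 patients and four questionnaire visits. The upper end applies only if the appended version or a translation of it is used.

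The primary endpoints and the sample size are not affected. The correction should be made, because this is the trial's only secondary endpoint and answers given on the wrong version cannot be collected again.

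**What to change.** Reconcile sections 10.2, 12.4.7 and 22.1:

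1. Replace the form in Appendix 1 with the Russian EQ-5D-5L form.
2. Name that version in section 12.4.7.
3. Obtain confirmation from both sites that this is the form in use.
4. If any Y-version forms have already been completed, record the version in the database and analyse those forms separately.

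The cost is one appendix change, one version name and an ethics committee submission under section 15.1. Visits and patient burden do not change. The schedule in section 21 runs from May 2024 to May 2029, so the earlier the sites are asked, the fewer forms can be affected.
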